
The overarching goal of this study is to build the most cost-effective adaptive implementation strategy involving REP and Facilitation to enhance the update of an EBP for mood disorder and subsequent changes in patient outcomes using clinical assessments available in routine care. The EBP, Life Goals (LG), is an evidence-based psychosocial treatment shown to improve outcomes among patients with mood disorders and will be implemented as part of routine clinical care at each organization. In this study, sites initially receiving REP that have not fully implemented LG (e.g., <10 patients receive the LG EBP) will be randomized to receive additional External Facilitation (**REP+EF**) or External plus Internal Facilitation (**REP+EF/IF**). At 12 months, sites that are non-responsive to External Facilitation (**REP+EF**) will be re-randomized to receive **REP+EF** or **REP+EF/IF** and then followed for another 12 months to determine whether longer-term exposure to Facilitation is needed. Because sites and not patients will be randomized, the EBP (LG) is already an established evidence-based clinical practice that will be implemented as part of routine clinical care, and because all sites will receive some additional state-of-the-art

implementation support through Facilitation, this project involves health care operations improvement within select healthcare systems.

Primary Study Aim. To determine whether sites that do not exhibit response to REP alone after 6 months (e.g., <10 patients receiving LG), the effect of adding an External and Internal Facilitator (**REP+EF/IF**) versus adding an External Facilitator alone (**REP+EF**) on use of the EBP (LG) and changes in routinely collected patient clinical assessments (health-related related quality of life and mood symptoms).

Secondary Aim 2. To estimate the costs of REP+EF/IF compared to REP+EF at the sites.

Secondary Aim 3. To describe the implementation of EF and EF/IF, including interaction between the two roles and the specific strategies EFs and IFs use to facilitate LG uptake across different sites.

Results from the project will be used to inform activities designed to implement promising ways to improve clinical care and healthcare operations.

III. Background and Significance

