Step 1: Provider Contact: EF sets measurable goals in LG uptake		√	√
Step 2: Technical assistance: EF makes structured calls to site’s LG providers, giving specific guidance on implementing LG components		√	√
REP+External and Internal Facilitator (REP+EF/IF)			
Step 1: Initiation: EF identifies IF within the site; IF meets with EF, LG provider, and leadership, establish measurable goals in LG uptake			√
Step 2: Relationship-building: IF identifies site priorities per leadership input, identifies other LG program champions		√	√
Step 3: Benchmarking and Ongoing Rapport: EF continues coaching IF, IF measures LG progress, IF develops rapport with leadership			√

Step 4: Cultural adaptation: IF uses local site culture knowledge to facilitate LG, addressing potential barriers, aligning LG goals with site			√
Step 5: Ongoing marketing and sustainability: IF, EF and LG provider summarize progress with leadership, develop business/training plans			√

REP LG Package: The LG REP package includes all of the components needed to implement LG, including the LG provider manual, group session scripts and focus points covered in each session in a semi-directed fashion, the registry template for monitoring mood and LG progress, scripts for follow-up calls, patient workbooks, and an implementation manual describing logistics (e.g., identifying group session rooms, identifying patients for LG, medical record templates for LG sessions, billing codes).

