LG fidelity: Because this study is designed to assess real-world implementation of routine clinical care, minimally invasive measures developed by study investigators will be used to assess use of LG services. LG providers will complete a computerized log of LG encounters, which will

ascertain the number of completed group sessions and provider follow-up contacts received by each patient. LG fidelity will also be assessed using a previously established measure that combines information from the LG provider logs with confirmatory information from patient surveys. The fidelity monitor calculates a total score based on number of group sessions (0-4) and follow-up contacts (0-6) completed by each patient. Average patient completion of group sessions of $\geq 75\%$ was associated with improved mental health-related quality of life.

Table 4: Recording Time Spent on REP, Facilitation, and LG

REP (all sites)
LG provider and site representative time spent at in-service, training
LG provider time spent with LG trainer on phone follow-ups, documentation
Project staff (investigators, personnel): Packaging LG, training, site contacts, note-taking
EF (REP+EF sites)
LG provider time spent with External Facilitators (phone contacts, email follow-ups)
LG provider actions taken to facilitate LG, documentation
Project staff (EF): Time spent with provider contacts, follow-up technical assistance, documentation of goals with each site
IF (REP+EF/IF sites)
Time IF spent with EF, LG providers in meetings and establishing goals, site priorities, develop rapport
Time IF spent working out LG barriers, strategizing and aligning LG goals with site goals
Time IF spends with EF and LG provider in summarizing implementation progress with leadership, business plan development
LG Implementation (all sites)
Group sessions: Number of outpatient clinic visits w/ LG patients actually completed
Follow-up contacts: Time spent on each contact
Other Face-Time: Any time spent seeing LG patients face-to-face or on phone outside of sessions/contacts
Phone Time: Any time spent on the phone only with LG patients. Include time spent leaving messages, playing "phone tag", etc.
Care Coordination: Any and all time spent on behalf of a LG patient when patient is not present (e.g., phone, consultation)
Charting Time: Any time spent charting for a LG patient (e.g., registry, progress notes, updating treatment plans, etc.)

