Implementation Strategy (REP, EF/IF) Use and Costs (Table 4): Personnel time is likely to account for the vast majority of costs associated with REP and Facilitation. All activities involving REP, EF, and IF will be documented using previously established log forms (e.g., R01 MH 79994) and all costs will be multiplied by personnel wage rates including fringe. We will estimate time costs incurred by both site employees as well as project staff (REP trainer, Facilitators). We chose to focus on a cost analysis from the perspective of the sites because the added cost of paying for and providing Internal Facilitation will be the major concern of these stakeholders, who are the target audience for potentially spreading value-based implementation frameworks

REP Costs from the site's perspective: We will estimate the costs of the REP implementation from the site's perspective by collecting information on the total time LG providers spent on 1) in-services, 2) training, and 3) monitoring by surveying the providers involved in each step based on the LG registry log.

REP and External Facilitation costs: Total costs of REP and EF implementation will be estimated based on study staff logs by summing up the total time spent by the study staff in LG package dissemination, in-services, training, and follow-up site calls and documentation.

Internal Facilitation Costs: IF costs are primarily borne by the site and are detailed in Table 4. Each IF will complete a log of activities using similar procedures in ROCC. The total time spent in IF activities will be multiplied by personnel wage rates.

LG Costs from the site's perspective will also be estimated for each site. Study staff will ascertain information from the LG provider registry on number and time for each group session, follow-up contact, as well as for additional provider and patient encounters and clinical documentation

(Table 4).

VI. Analyses and Evaluation

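### Table 4's Internal Facilitation block logs only the Internal Facilitator's own hours and no facilitation row captures leadership time, so Secondary Aim 2 risks understating the site cost of REP+EF/IF

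*Combined protocol and SAP*

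**What the plan says.** Secondary Aim 2 (Section II) is "To estimate the costs of REP+EF/IF compared to REP+EF at the sites". Section V.F takes the site's perspective because paying for Internal Facilitation is expected to be what sites care about most.

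Table 4 lists the time to be recorded, by component. The block for External Facilitation is headed "EF (REP+EF sites" and has two rows for site staff: "LG provider time spent with External Facilitators (phone contacts, email follow-ups" and "LG provider actions taken to facilitate LG, documentation". The block for REP+EF/IF sites has three rows. The first is "Time IF spent with EF, LG providers in meetings and establishing goals, site priorities, develop rapport", the second is the IF's time on barriers and on aligning goals, and the third is "Time IF spends with EF and LG provider in summarizing implementation progress with leadership, business plan development". The REP and LG Implementation blocks are marked for all sites.

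Table 1 (Section V.E) describes IF steps that involve other people at the site. Step 5, for example, reads "IF, EF and LG provider summarize progress with leadership, develop business/training plans".

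The paragraph on Internal Facilitation costs (Section V.F) points to Table 4 for the detail, says each IF keeps a log, and continues: "The total time spent in IF activities will be multiplied by personnel wage rates". The general costing paragraph just before it commits to logging all REP, EF and IF activities and to costing the time of site employees and project staff. Table 3 gives staff, LG provider and facilitator logs as the sources for facilitation costs.

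**The concern.** A site-perspective cost comparison needs the same categories of person counted in both arms. Internal Facilitation works by drawing on people other than the IF, and leadership above all. If the recording sheet has a field for the IF's hour in a leadership meeting but none for the leader's hour, the site has borne a cost that the analysis never sees.

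The omission would not cancel. Leadership contact about LG is meant to occur under REP+EF/IF. At EF-only sites, the contamination paragraph in Section V.E treats contact with leaders as an IF component that should be avoided. Missing leadership hours therefore lower the REP+EF/IF increment. That increment is also the numerator of the cost-effectiveness ratio in Section VI, so for any positive gain in utility the ratio would look more favourable than it is. Hours not logged at the time are hard to recover later.

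**Working it through.** The plan gives no cost total that depends on this point. The $5,500 per site for IF in the earlier randomised study (Section IV) comes without hours or wage rates, so it cannot be rebuilt. The check is a reading of the tables against each other, followed by an illustration of scale.

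**1. Who is counted in Table 4**

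| Block | Sites named | IF time | LG provider time | Leadership or other site staff time |
|---|---|---|---|---|
| REP | all | none | yes | site representative, at in-service and training only |
| EF | REP+EF | none | 2 rows | none |
| IF | REP+EF/IF | 3 rows | none | none |
| LG Implementation | all | none | delivery of LG | none |

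The REP and EF blocks name other site staff where their time is to be counted. The IF block mentions the LG provider and leadership only as people the IF meets.

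**2. Who takes part in Internal Facilitation (Table 1)**

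- Step 1: IF, EF, LG provider and leadership meet.
- Step 3: the EF coaches the IF, and the IF builds rapport with leadership.
- Step 5: IF, EF and LG provider report progress to leadership.

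These three steps are ticked only for REP+EF/IF. Step 2 also draws on leadership input, but in the available text it is ticked for both facilitation arms, so nothing here rests on it. The fidelity paragraph in Section V.E counts leadership meetings held by the IF and EF, which confirms that they are expected. It gives neither their number nor their length.

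**3. Is there another route for the missing hours?**

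- LG provider time on EF calls: yes, if the EF rows are also used at REP+EF/IF sites. Table 1 ticks both EF steps for that arm, and Section VI sums REP, EF and IF costs for each site.
- LG provider time with the IF alone: Table 3 names LG provider logs, so a source exists, but no Table 4 row asks for it.
- Leadership time: none of the three logs in Table 3 is kept by leadership, and no facilitation row asks for it.

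**4. Scale (leadership time only)**

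The hours and wages below are assumptions. Only the $5,500 is from the documents.

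- Low: 3 h × $60 = $180; 180 / 5,500 = 3.3%.
- High: 6 h × $100 = $600; 600 / 5,500 = 10.9%.

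The $5,500 covers twelve months, while a facilitation phase in this trial lasts six. Halving it to $2,750, which assumes even spending, gives 180 / 2,750 = 6.5% and 600 / 2,750 = 21.8%. LG provider time with the IF outside EF contacts would add to these figures, but the documents offer nothing to size it.

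**The case against.** The strongest reply is that Table 4 is a summary and the surrounding text already covers the ground. Section V.F promises to document every REP, EF and IF activity and to cost site employees' time, and leaders are site employees. The IF costing sentence does not limit itself to the IF's own hours. The established log forms are not reproduced and may already record who attended and for how long. The IF may be the clinic director (Section V.E), in which case that leader's time is already IF time. Section VI calls the incremental comparison exploratory, and the primary outcome is untouched.

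Much of this stands, and it limits the point. It does not remove it: a general promise with no row and no named source for leadership hours conflicts with a table to which the IF costing paragraph expressly refers.

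Two stronger readings are tempting, and the documents support neither.

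- A reader might infer that only the IF's hours are costed at REP+EF/IF sites. That describes the IF block, not the table: the REP and LG Implementation blocks apply to all sites.
- A reader might take the EF block's heading literally and infer that the whole EF component is missing from REP+EF/IF sites. At six one-hour monthly calls, that would drop at least 6 LG provider hours per site from one arm only. Table 1 and the per-site summation in Section VI contradict this. Both arms have monthly calls of about an hour, so on the natural reading that time is recorded in both and largely cancels.

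**Conclusion.** The point holds in a limited form. The IF block records only the IF's time, and no facilitation row records leadership time or LG provider time with the IF outside EF contacts, although Internal Facilitation uses leadership time by design. Recording time as Table 4 is written risks understating the site cost increment of REP+EF/IF over REP+EF. The direction is clear, but that an understatement will occur is not established, because the text commits to costing site employees' time and the log forms are not shown.

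The illustration of $180-600 per site, about 3-11% of the twelve-month IF cost, rests wholly on assumed hours and wages. It would be smaller where the IF is the clinic director. Sites that move from REP+EF to REP+EF/IF at Month 12 would carry the same gap, so a comparison by Month 6 assignment would be affected somewhat less. The mismatch between the EF heading and Table 1 is a separate, plain inconsistency. This is a cheap improvement to a secondary aim and does not threaten the trial's main comparison.

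**What to change.** 1. Retitle the EF block in Table 4 as *EF (REP+EF and REP+EF/IF sites)*, to agree with Table 1.
2. Add two rows to the IF block: *LG provider time with the IF outside EF contacts*, and *site leadership and other site staff time in IF meetings (number attending × duration)*. Both can be entered in the log the IF already keeps. Leadership meetings are already counted for fidelity, so the second row adds only attendance and length.
3. In the Internal Facilitation costs paragraph of Section V.F, state that IF cost is the time of all site staff in IF activities, each multiplied by their own wage rate, and that no hour is counted in both the EF and IF blocks. An LG provider's hour on a joint call with the EF stays in the EF row.

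The cost is two log fields, one relabelled heading and a sentence or two of text. The downside is slightly more logging for the IF and a less favourable cost figure for REP+EF/IF.

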Fidelity/cost measures for REP, EF, and IF were also operationalized based on careful observation, review of study staff and provider logs, and clarification of EF/IF roles via expert panel input. These tools were used in the R01 to monitor potential contamination across EF/IF roles as well as competence. IF costs were estimated using monthly provider logs. Total costs for IF for each site was \$5,500 over the 12-month period, and involved specific activities listed in Table 1. Nonetheless, the value of IF in addition to EF has not been assessed in a fully powered clustered randomized controlled trial.

V. Methodology

Overview: This is an adaptive implementation study involving cluster randomization at the site level of previously established implementation strategies designed to implement promising ways to improve health care operations. Providers will implement an EBP (Life Goals) as part of routine clinical care and no patients will be randomized. Outcomes data include site-level use of the EBP as well as assessments already available as part of routine clinical care (e.g., symptoms, quality of life).

A total of 80 community-based clinics (sites) from Michigan (MI), Colorado (CO), or Arkansas (AR) that provide care for persons with mood disorders (depression or bipolar disorders) for a total of 1,600 patients with mood disorders (N=20 per site). The primary aim of this study will determine whether non-responsive sites (i.e., limited LG uptake) randomized to receive REP and additional Internal and External Facilitation (**REP+EF/IF**) implementation strategies to help adopt an EBP (Life Goals-LG) versus sites randomized to receive REP and additional External Facilitation only (**REP+EF**).

A. Site study population: Site inclusion criteria include the following:

1. Community-based mental health or primary care clinic located in MI, AR, or CO with at least 100 unique patients diagnosed with or treated for mood disorders in a given year (to ensure adequate patient N).
2. Availability of a bachelor's or master's level health care provider with a mental health background and experience with implementing group sessions (core modality of LG) who can be trained to provide LG to up to 20 adult patients with mood disorders in the clinic in a one-year period.
3. Availability of an employee at the site with direct reporting authority to the leadership of the site and network who could serve as potential internal facilitator.

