C. Study Design flow. Primary care or mental health outpatient clinics agreeing to participate will be randomly selected (N=80 total) and initially offered REP for six months in order to implement LG. Based on previous research and preliminary data, it is expected that after six months of REP at least two-thirds of sites will be non-responsive to REP. The primary focus of the randomized comparisons in this study are sites that are initially non-responsive to REP (k=40), defined based on our preliminary studies as <10 patients receiving LG within six months of initiating REP and that patients received <75% group sessions. (Although not part of the primary randomized comparisons, sites that are responsive at 6 Months will continue to be followed and outcomes will be assessed). The non-responsive sites will be randomized 1:1 to receive additional External Facilitation (**REP+EF**) or External plus Internal Facilitation (**REP+EF/IF**). After another six months (at Month 12), sites that are still non-responsive (based on the same criteria) will be randomized 1:1 to either continue **REP+EF** or augmentation with IF (**REP+EF/IF**). All sites are followed for a total of 24 months. Patient-level outcomes will be assessed by study staff using assessments considered part of routine clinical care (e.g., symptoms and quality of life) starting at the initiation of REP and then at 6, 12, 18, and 24 months later among a pre-selected cohort of n=20 patients per site who are identified by site providers for LG (total patients participating in the project N=k*n=800). Patients receiving Life Goals as part of their routine clinical care may opt in or out in participating in the outcomes assessment component. As with our prior implementation work (R01 MH79994), independent evaluators (study staff who are not aware of the assignment to **REP+EF** or **REP+EF/IF**) will conduct study outcomes assessments to ensure consistency of

data collected across sites and to prohibit provider/site or investigator assessment bias. Pre-identification of LG recipients also maximizes consistency of the patient population across sites (see patient criteria below).

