Intent-to-treat. Every effort will be made to collect patient level outcomes across all 80 sites and patients (N=1600) to conduct the primary and exploratory analyses (see below). The 40 sites randomized at month 6 (total 800 patients) will be included in the intent-to-treat randomized sample. The Primary Aim analysis will compare strategies in non-responding sites (k=40) beginning with **REP+EF/IF** versus strategies beginning with **REP+EF** on longitudinal change in patient-level SF-12 mental health scores (MCS- primary outcome). This analysis is a comparison of cells A+B+C vs. D+E (Figure 2). For this analysis, the longitudinal outcome is SF-12 mental health scores measured at Months 6 (pre-randomization), 12, 18, and 24. The primary contrast is the between groups difference in change from Month 6 to Month 18. The follow-up contrast at Month 24 will also be examined in this and all subsequent analyses. Linear mixed models (LMM), also known as random effects models, fit with SAS PROC MIXED will be used to analyze the longitudinal data. LMMs use all available measurements, allowing subjects to have an unequal number of longitudinal observations and producing unbiased parameter estimates as long as unobserved values are missing at random. The analysis will fit a 3-level (repeated measures for each person clustered within site) LMM with fixed effects for the intercept, time, group, and a group-by-time interaction term, where group is an indicator of **REP+EF/IF** vs. **REP+EF**. The LMM will also include random effects for site and time, an unstructured within-person correlation structure for the residual errors, and it will adjust for the following pre-randomization measures collected through Month 6: state and type of practice (primary care- or mental health site). Model diagnostics will be used to determine the suitability of more parsimonious (e.g., autoregressive) correlation structures, and nonlinear (e.g., piecewise linear or quadratic) effects for time. LMMs similar to the above for the primary outcome will be conducted for the secondary outcomes: **REP+EF/IF** vs. **REP+EF** on change in number of LG encounters, functional impairment, and psychiatric symptoms.

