The goal of the Secondary Aim 1 analysis is to determine whether continuing **REP+EF** versus augmenting with **REP+EF/IF** leads to changes in outcomes, among sites who are non-responsive at Month 12. This analysis is a comparison of cells B vs. C (Figure 2). Both primary and secondary longitudinal outcomes above will be examined using an LMM similar to that described above, except (a) including only the subset of sites that do not respond at Month 12 to **REP+EF**, (b) using monthly longitudinal outcomes from Month 12 to Month 24, and (c) the LMM will use dummy-indicators for time (i.e., time-saturated model since there are only 3 measurement times for each longitudinal outcome).

The Secondary Aim 2 analysis will involve an analysis of implementation costs. The implementation (REP, EF, IF) costs will be summed for each site as a measure of total costs and changes in costs will also be assessed over time (6, 12, 18, 24 months). An exploratory analysis of the incremental effectiveness of IF by comparing costs from sites given **REP+EF/IF** versus those with **REP+EF** will be conducted from the site's perspective. In regression models of costs, Generalized Linear Models with log link functions will be used to correct for heteroscedasticity and reduce the impact of outliers. Effectiveness will be measured by changes in health utilities using the SF-6 (a subset of SF-12 questions) as well as the Euro-QOL 5D. Cost-effectiveness will be calculated as the ratio of incremental average site-level cost and incremental average effectiveness (change in patient-level utilities) of IF. A standard nonparametric bootstrapping approach will be used to calculate confidence intervals and cost-effectiveness acceptability curves.

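### The Primary Aim asks about External Facilitation alone, but the Month 18 primary contrast compares strategies that begin with each option, and no contrast is planned at Month 12

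*Combined protocol and SAP*

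**What the plan says.** All references are to the combined protocol and SAP.

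- **The question.** Section II (Primary Study Aim) sets REP+EF/IF "versus adding an External Facilitator alone" in sites that have not responded to REP. Section V (Overview) repeats it: "versus sites randomized to receive REP and additional External Facilitation only".
- **The Month 12 step.** Section II introduces a second randomisation: "At 12 months, sites that are non-responsive to External Facilitation" are randomised again. Section V.C gives the allocation. These sites "will be randomized 1:1 to either continue" REP+EF or have IF added.
- **The primary analysis.** Section VI (Intent-to-treat) says: "The Primary Aim analysis will compare strategies in non-responding sites (k=40) beginning with" REP+EF/IF against those that begin with REP+EF. It then gives the cells, "This analysis is a comparison of cells A+B+C vs. D+E", and the time point: "The primary contrast is the between groups difference in change from Month 6 to Month 18". Month 24 is named as a follow-up contrast. No Month 12 contrast is named, although Month 12 scores enter the model.
- **The cells.** Section VI (Secondary Aim 1) compares B with C among the Month 12 non-responders to REP+EF. Its wording suggests that C is the augmented cell. Figure 2 is not shown, so this is inferred. Nothing below depends on it, because both cells sit in the REP+EF group.

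**The concern.** The document states two different questions. Sections II and V ask what the Internal Facilitator adds to External Facilitation. The Month 18 contrast asks whether it is better to start with both facilitators, or to start with External Facilitation and step up about half of the sites that do not respond. Both questions are sensible, but the second does not answer the first.

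Section V.E describes the Internal Facilitator's work over a six-month period. By Month 18 the augmented sites have therefore had one such period while still being analysed as REP+EF. If IF works, this moves the two groups closer together.

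The risk lies in interpretation. A reader who takes the question from the Primary Aim could read a null Month 18 result as evidence that IF adds nothing to EF, and the contrast cannot support that alone. Section V.F says that IF costs fall mainly on the sites and that these costs are the stakeholders' major concern, so such a misreading would have practical consequences.

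**Working it through.** **Inputs from the documents.** 40 randomised sites with 20 patients each (sections V.C and VI); 1:1 allocation at Month 6, so about 20 sites per arm; 1:1 re-randomisation of REP+EF non-responders at Month 12. The plan's own total reproduces: 40 × 20 = 800 patients. No power, effect size, SD or intraclass correlation is given, so there is no planned figure against which to set a loss of power.

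**Assumptions.**
- *r*, the Month 12 non-response among REP+EF sites. In the pilot (section IV), three of four sites did not respond to REP, and two more responded once EF was added. Two of those three gives r = 1/3. The document's own 50% (two of all four) gives r = 1/2.
- *f*, the fraction of the IF effect that an augmented site has gained by Month 18. It is shown at 1 and 0.5.
- The effect δ of EF/IF versus EF alone is the same in all sites.

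**Formulas.** Augmented sites = 20 × r/2. Their share of the REP+EF arm = r/2. That arm's mean moves by f × (r/2) × δ, so the Month 18 contrast is δ × (1 − f × r/2).

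| r | Augmented sites (patients) | Share of arm | Kept, f = 1 | Kept, f = 0.5 |
|---|---|---|---|---|
| 1/3 | 3.3 (67) | 17% | 83% | 92% |
| 1/2 | 5 (100) | 25% | 75% | 87.5% |
| 3/4 | 7.5 (150) | 37.5% | 62.5% | 81% |
| 1 (ceiling) | 10 (200) | 50% | 50% | 75% |

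The first two rows follow the pilot. The last two show how the result moves if non-response is higher.

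**Does another planned analysis answer the stated question?**
- *Month 24:* no. IF entered the comparator arm a year earlier.
- *Secondary Aim 1 (B versus C):* no. It is randomised and tests added IF, but only in Month 12 non-responders, about 20 × 1/3 = 6.7 to 20 × 1/2 = 10 sites in total.
- *Month 12:* the data exist. Section V.D stratifies the second randomisation by site quality of life measured at Month 12, so that assessment comes before any REP+EF site is assigned IF. No contrast is planned there.

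**Would a Month 12 estimate come out of the primary model as written?** Section VI has a time effect and a group-by-time term, with piecewise or quadratic forms left to diagnostics, so the default appears to be linear. With slope difference β per month, the Month 6-to-12 difference is 6β and the Month 6-to-18 difference is 12β. The first is always half the second and gives no separate information on Month 12.

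**The case against.** The strongest reply is that the plan already names its estimand. The sentence just before the list of cells describes strategies by how they begin. Section II sets out the second randomisation before it states the Aim, and its declared goal is an adaptive strategy. The Overview speaks of sites randomised to receive each option, which fits analysis by Month 6 assignment. This stands: the pooling is disclosed and correct. It does not remove the gap, because the Aim and the Overview still say alone and only.

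A reader might infer that Month 18 is confounded, or that the augmented sites should be removed. The documents support neither. Those sites reached their cell by randomisation within the strategy, and dropping them would under-represent non-responders.

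Secondary Aim 1 would be read beside a null primary result and bears on added IF. That also stands, but only for a small subset of sites that start IF late.

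Month 12 is not the only route to an EF-alone comparison. Cells A and B at Month 18, with B weighted by 2 (the inverse of its 1/2 re-randomisation probability), would estimate it too. Month 12 is also early. Section V.E has the Internal Facilitators trained only after randomisation, and Life Goals itself runs for four weekly group sessions followed by six weekly contacts, so patient scores may lag. This is a fair limit on the Month 12 contrast and a reason to keep it secondary.

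The pilot rates rest on three or four sites and on a three-month response window, whereas the trial uses six months. The percentages are therefore illustrations, not forecasts.

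**Conclusion.** The point holds as a mismatch between the question stated in sections II and V and the quantity estimated in section VI. The primary analysis is not in error. Month 18 is a sound first-stage intent-to-treat contrast, but no planned analysis gives an EF/IF-versus-EF-alone estimate across all the randomised sites.

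At 33-50% Month 12 non-response and with an equal effect across sites, the Month 18 contrast keeps 75-83% of that effect if IF is fully effective within six months, and 87.5-92% if it is half effective. Higher non-response would lower these figures.

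A reader might be tempted to turn this into SF-12 points with the 1.22 reported for the earlier trial in section IV. That figure comes from REP+EF/IF versus REP alone, a different comparison, so the documents give no basis for a loss in points. Nor do they show that the result will be misreported, only that the Aim's wording invites it.

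**What to change.** Keep the Month 18 primary contrast, and keep every augmented site in it.

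1. Pre-specify the between-group difference in change from Month 6 to Month 12 as a named secondary contrast, the comparison of EF/IF with EF alone in all randomised sites. Estimate it with categorical time, in the primary model or in a companion model, so that it rests on the Month 12 data.
2. Reword the Primary Aim, the Overview and the conclusion that they support to match section VI: strategies that begin with REP+EF/IF against strategies that begin with REP+EF, with IF added for about half of the Month 12 non-responders to REP+EF.

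No new data, sites or visits are needed. The costs are one more secondary contrast to report and either a change to the time coding of the primary model or a second model. The Month 12 result would also need the caveat that it reflects only six months of facilitation.
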